**[name]**  
Senior Research Scientist  
Department of Research

February 15, 2019

Dear Clinicaltrials.gov administration,

This cover letter accompanies a protocol being submitted for NCT02998372. The study is supported by an NIH grant (R21 AR069150). The study primarily focuses on computational simulation of function for knees with patellar instability. For validation of the models, simulated data was compared to pre-operative and post-operative measures of patellar tracking and patellofemoral contact pressures determined by computational reconstruction of functional activities performed by patients during MRI scans. Prior to the proposed study, imaging with accompanying kinematics, pressure data and computational models was available for seven subjects being treated for patellar instability. The grant application proposed adding 5 additional subjects and models to the study. Because the subjects would be evaluated pre-operatively and post-operatively, the study was designated as a clinical trial, although the surgical approach was left up to the surgeon as opposed to being specified within the protocol. Therefore, the study was registered on clinicaltrials.gov based on the aims and goals listed for the grant application.

Patient enrollment has now been completed for the study. Only three of the proposed five subjects that were to be evaluated pre-operatively and post-operatively were enrolled. Additional pre-operative imaging from other sources was used to complete creation of the necessary number of models.

The attached protocol is an abbreviated version of the NIH grant application that includes the development of computational models and the analysis of the five subjects. That is the clearest document to describe the relationship between the clinical trial portion of the study and the overall stated goals.

Please let me know if you have any questions about this document.

Sincerely,

A handwritten signature in black ink that reads "[name]".

[name]

# Computational Simulation of Patellar Instability

## Specific Aims

### 1. Dynamic computational simulation of patellar instability

Use multibody dynamic computational simulation to replicate lateral patellar maltracking in patients being treated for patellar instability. Knee models representing patients with recurrent instability will be used to characterize patellar lateral maltracking and pressure applied to patellofemoral cartilage during simulated functional activities. The models will be individually validated against previously acquired and newly generated data from in vivo motion. The source of the in vivo data will be computational reconstruction of in vivo function performed with the patients that the simulation models are based on.

### 2. Characterize influence of surgical stabilization on knee function for individual patients

The multibody dynamic models will be used to simulate MPFL reconstruction and tibial tuberosity medialization. MPFL reconstruction will be simulated with variations in the femoral attachment position, while the magnitude of tuberosity realignment will be varied. The actual surgical procedures performed on the patients will be simulated, with the influence on lateral tracking and contact patterns compared to in vivo results to validate simulation of the surgical procedures.

### 3. Compare surgical options as a function of patellofemoral anatomy

Variations in patellar tracking and contact pressure will be compared between MPFL reconstruction and tuberosity medialization. Techniques to alter trochlear dysplasia and tuberosity lateralization will also be developed and applied to the models. Simulations performed while varying anatomy will establish ranges over which each surgical option limits patellar maltracking without elevating contact pressures.

## Approach

### Aim 1: Simulation of instability

Models for dynamic simulation of knee function will be developed to represent 12 knees with recurrent patellar instability. Simulation of motion will be performed using multibody dynamics software. Springs will be used to represent the anterior and posterior cruciate ligaments, the medial and lateral collateral ligaments, the posterior capsule, the patellar tendon, and the lateral and medial retinaculum. Quadriceps muscle forces will be applied to the patella through springs representing the quadriceps tendon. Medial and lateral hamstrings forces will apply one-third of the quadriceps force to the tibia along the long axis of the femur.

Solid bodies representing the femur, patella, and tibia will include the corresponding cartilage for each bone. Cartilage contact at the tibiofemoral and patellofemoral articulations will be governed by simplified Hertzian contact. Patellofemoral and tibiofemoral kinematics and detailed pressure maps will be characterized during post-processing by applying rigid body translations and rotations exported from the simulation to the bone models, reproducing the simulated joint motion. At flexion angles with the patella engaged with the trochlear groove, starting at 15°, muscle and ligament force vectors exported from the simulation will be applied to the patella. Overlap between cartilage on the femur and patella will be combined with the elastic modulus and Poisson's ratio of the cartilage to determine reaction forces on elements on the surface of the patella based on linear elastic theory, referred to as the discrete element analysis technique. The position of the patella within the trochlear groove will be iteratively modified until the joint compression, lateral force and tilt moment are balanced, producing a pressure pattern based on the applied force and area for each element. Tibiofemoral and patellofemoral kinematics will be quantified from the motion of local coordinate axes embedded in each bone based on anatomical landmarks using the floating axis coordinate system.

High resolution MRI scans of subjects with patellar instability are currently available for 7 subjects from a previous study (3T scanner, extremity coil, proton density-weighted images, sagittal plane, 0.3 mm in plane resolution, 1.5 mm slice thickness). Models will be reconstructed from these scans, allowing representation of cartilage surfaces and attachment points for the ligaments, patellar tendon, and quadriceps tendon. Five additional subjects scheduled for surgical stabilization for recurrent patellar instability will be recruited to meet the proposed sample size of 12 models.

The 5 recruited subjects will participate in pre-operative computational reconstruction of in vivo knee function with closed chain loading conditions. The technique uses high resolution MRI scans to create computational models of the femur, patella and tibia, as well as the cartilage. Low resolution scans are acquired during isometric quadriceps contraction with the knee positioned at multiple flexion angles, with the aid of a MRI-compatible loading frame that applies a spring-loaded force of 60 N to 85 N along the axis of the body at the foot. Shape matching algorithms align models of the bones from the high resolution images, with attached cartilage, to bones reconstructed from lower resolution scans with the knee flexed.

Models of each knee will be used to simulate the in vivo function. The muscle forces will be ramped up until the

reaction force at the foot reaches the spring force applied in vivo. A direct comparison of tibiofemoral and patellofemoral kinematics and contact pressures between computational and in vivo data will be performed. The accuracy of computational simulation will be reported in terms of root mean square errors between the computational and in vivo data, along with correlation coefficients evaluating the accuracy of variations in output related to changing the flexion angle and between knees. Once the pre-operative models are validated by comparison to the output from reconstruction of in vivo function, they will be used to represent a dynamic squatting

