### **Aim 2: Simulation of surgical stabilization**

Accuracy of the post-operative models will be assessed in the same manner as the pre-operative models. The newly enrolled subjects will be treated surgically, with the procedure performed based solely on clinical evaluation, and will participate in post-operative computational reconstruction of in vivo knee function. All models will be modified to represent the post-operative condition based on the imaging data and the surgical notes. The post-operative models will be used to simulate function and compare kinematics and contact pressure data to the data determined from the subjects.

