### **Aim 3: Compare surgical options**

The simulation models will be used to represent two primary surgical options: reconstruction of the medial patellofemoral ligament and realignment of the tibial tuberosity, while also varying parameters related to knee anatomy. The kinematics and pressure output from all the simulated surgical variations will be compared between the 12 models at individual degrees of knee flexion with repeated measures ANOVA's combined with post-hoc Student-Newman-Keuls tests, with significance set at  $p = 0.05$ . The analyses will focus on relative variations in the kinematics and pressure measurements, with the pre-operative condition treated as the control for each knee, with the goal of each procedure to reduce lateral patellar shift and tilt without increasing the contact pressure.

Analyses will be performed for various combinations of tibial tuberosity position and depth of the trochlear groove. For each combination, the statistical analyses noted above will be performed to compare the influence of the various surgical procedures on patellar tracking and contact, with an emphasis on determining the limits at which each procedure becomes ineffective in reducing lateral tracking without overloading cartilage. In addition, for each procedure multivariable linear regression analyses will be performed to relate the anatomical parameters to the change in the output parameters.

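### RMSE and correlation cannot isolate or quantify an error in how strongly the models respond to anatomy, on which the Aim 3 ranges and slopes rely

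*Combined protocol and SAP*

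**What the plan says.** In the Approach, Aim 1 names two accuracy measures in a single sentence. The first concerns the size of the error: "The accuracy of computational simulation will be reported in terms of root mean square errors between the computational and in vivo data". The second, which completes that sentence, concerns association: "along with correlation coefficients evaluating the accuracy of variations in output related to changing the flexion angle and between knees". It does not give the type of correlation, or say whether it is taken at one angle or pooled over angles. The models move on to further use "Once the pre-operative models are validated by comparison to the output from reconstruction of in vivo function", but neither measure has a numerical limit. For the operated state, Aim 2 says that "Accuracy of the post-operative models will be assessed in the same manner as the pre-operative models". Specific Aim 2 adds that the procedures the patients actually received will be simulated and their effect set against the in vivo findings.

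Specific Aim 3 states that "Simulations performed while varying anatomy will establish ranges over which each surgical option limits patellar maltracking without elevating contact pressures". The Approach, Aim 3, says how: "Analyses will be performed for various combinations of tibial tuberosity position and depth of the trochlear groove", with repeated measures ANOVA and post-hoc tests for each combination. On scale: "The analyses will focus on relative variations in the kinematics and pressure measurements, with the pre-operative condition treated as the control for each knee". For each procedure, "multivariable linear regression analyses will be performed to relate the anatomical parameters to the change in the output parameters".

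The plan contains no mean signed error, no slope of simulated against in vivo output, and no comparison of simulation error with tuberosity position or groove depth.

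**The concern.** Aim 3 changes two anatomical features inside each model and asks where a procedure stops helping. The answer depends on how fast the simulated output moves as the feature moves. The validation in Aims 1 and 2 asks something different: how close the output is overall, and whether it ranks angles and knees in the right order.

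Correlation is offered as the check on variation between knees, but it ignores the size of that variation. RMSE responds to size, but it adds rate error to scatter and to constant offset. The distinction matters because an offset that is the same before and after surgery drops out of a change from the pre-operative state, while a rate error need not. If the response to anatomy is mis-scaled relative to the surgical effect, the Aim 3 limits move and the regression slopes are wrong, and the reported accuracy figures would not show which error was present.

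**Working it through.** **Inputs.** From the documents: the two measures (Aim 1), their reuse (Aim 2), the change-from-pre-operative scale (Aim 3), 12 planned models made up of 7 existing and 5 recruited knees, and 3 of those 5 enrolled (cover letter). The documents give no SD, expected RMSE, expected correlation or acceptance limit, so there is no plan figure to reproduce. All values of b, r, SD and scatter below are assumptions. Change is read as a difference. If it meant a ratio, a common scale factor would cancel and an offset would not.

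**1. Correlation and rate.** Let simulated = b × in vivo, without scatter. Then r = 1.0 for every b from 0.25 to 2, while RMSE = |1 − b| in vivo SDs (0.5 SD at b = 0.5, and again at b = 1.5). Correlation is blind to the rate error; RMSE is not, but it gives no direction.

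**2. RMSE does not identify the source.** Set the in vivo SD to 1. With slope b of simulated on in vivo and correlation r, the simulated SD is s = b/r, and

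RMSE² = offset² + (s − 1)² + 2s(1 − r).

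| r | b | s | RMSE, no offset |
|---|---|---|---|
| 0.9 | 0.5 | 0.556 | 0.556 |
| 0.9 | 0.75 | 0.833 | 0.441 |
| 0.9 | 1 | 1.111 | 0.484 |
| 0.8 | 0.5 | 0.625 | 0.625 |
| 0.8 | 1 | 1.250 | 0.750 |

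At r = 0.9, the offset that brings the correct-rate model to the RMSE of the half-rate model is √(0.556² − 0.484²) ≈ 0.27 SD. The two models then report the same r and the same RMSE, yet only the half-rate model has an error that can survive differencing. At fixed r = 0.8 the half-rate model has the lower RMSE.

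**3. On a millimetre scale.** Assume an in vivo between-knee SD of 4 mm and scatter SD σ. Then r = 4b/√(16b² + σ²) and RMSE = √(16(1 − b)² + σ²).

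- σ = 1: b = 1 gives r = 0.97, RMSE 1.00 mm; b = 0.6 gives 0.92, 1.89 mm; b = 0.5 gives 0.89, 2.24 mm.
- σ = 2: b = 0.6 gives r = 0.77, RMSE 2.56 mm.

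**4. Pooling.** If correlation is pooled over 12 knees and 5 angles, with flexion variance four times knee variance and noise SD 0.4 (simulation), mean r is 0.984 at b = 1, 0.961 at b = 0.5 and 0.887 with no between-knee response at all. RMSE goes 0.399, 0.636, 1.060.

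**5. Consequence for Aim 3.** Suppose the surgical effect at reference anatomy is right, the response to anatomy is linear but scaled by b, and the limit is where the effect reaches zero. The limit then lies at 1/b of its true distance from reference: 1.67 times at b = 0.6, 0.67 times at b = 1.5. If instead all output is scaled by one factor, each test statistic is a ratio in which the factor cancels, so p-values do not change. The anatomy regression slopes are still wrong by that factor.

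**6. What a slope could show.** The 95% half-width relative to the slope is t(n − 2) × √((1 − r²)/(n − 2))/r. For n = 10 and r = 0.9: 2.306 × √(0.19/8)/0.9 = 0.39. At r = 0.8 it is 0.61. For n = 12 the values are 0.34 and 0.53.

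**The case against.** Several stronger readings are tempting and do not survive.

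- A reader might infer that the planned measures are blind to a rate error altogether. They are not. RMSE is planned, and with 1 mm scatter it rises from 1.00 to 1.89 mm as b falls from 1 to 0.6, with r also falling. What is missing is attribution and size.
- A reader might infer that a mis-scaled model would be accepted as accurate. The plan sets no acceptance limit, so the documents do not say what would be accepted.
- A reader might infer that every Aim 3 range is misplaced. Limits set by significance alone do not move under uniform scaling, and the plan does not say how a limit is set. The 1/b shift needs all the conditions in step 5, none of which the plan states. The b that compresses spread between knees also need not equal the b that governs response to an imposed alteration.
- A reader might infer that response to altered anatomy is never tested. The post-operative comparison in Aim 2 tests response to the procedures performed, which bears on tuberosity position where the tuberosity was moved. The check is only partial. The procedure was left to clinical judgement, post-operative in vivo measurement is described only for the newly enrolled subjects (three, per the cover letter), and the comparison does not relate error to groove depth.

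It is also fair to say that the document is an abbreviated grant application, and that slopes from about 10 knees will be imprecise. Both points stand. Imprecision is, however, a reason to show the interval, because the interval tells the reader how little the validation can exclude.

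**Conclusion.** The concern holds in a limited form. As planned, the accuracy measures cannot distinguish or quantify an error in the models' rate of response, and no step checks simulation error against the two features that Aim 3 varies. Identical r and RMSE can come from a half-rate model or from a correct-rate model with a 0.27 SD offset (at r = 0.9).

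The effect on Aim 3 depends on the form of the error. Mis-scaling relative to the surgical effect shifts the limits and biases the regression slopes; uniform scaling biases the slopes only. The 1.67-fold shift at b = 0.6 is an illustration, not an estimate. The documents do not show that the models are in fact mis-scaled. All SDs, scatter and values of b and r are assumed, and change is taken as a difference. This is an inexpensive improvement that bears on how far the Aim 3 ranges are supported.

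**What to change.** At each in vivo flexion angle, with the knee as the unit, report alongside RMSE and correlation:

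1. the mean signed error and the slope of simulated on in vivo output, with 95% intervals;
2. the regression of signed error (simulated minus in vivo) for shift, tilt and pressure on native tuberosity position and groove depth, with intervals;
3. the signed error in the pre-to-post change for knees measured in both states.

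If error trends with anatomy, or the interval is too wide to exclude a material trend, state that the Aim 3 ranges and slopes are not validated against in vivo response to anatomy. Say beforehand what trend would count as material.

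The direction of the slope matters. In the 4 mm model with 2 mm scatter, in vivo on simulated gives 16b/(16b² + 4): 0.98 at b = 0.6 but 0.80 at b = 1, so it would flatter the wrong model. Simulated on in vivo recovers b, provided the in vivo values are treated as the reference without error. Comparing between-knee slopes with slopes from imposed alterations is not advised, because knees differ in other ways that an imposed alteration holds fixed.

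The cost is a few regressions on data the plan already produces, with no new subjects or scans. The downside is precision: with about 10 knees (assumed: 7 existing plus 3 enrolled) and two anatomical predictors, only large errors can be excluded, and the validation claim may become more modest.

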### **Aim 2: Simulation of surgical stabilization**

Accuracy of the post-operative models will be assessed in the same manner as the pre-operative models. The newly enrolled subjects will be treated surgically, with the procedure performed based solely on clinical evaluation, and will participate in post-operative computational reconstruction of in vivo knee function. All models will be modified to represent the post-operative condition based on the imaging data and the surgical notes. The post-operative models will be used to simulate function and compare kinematics and contact pressure data to the data determined from the subjects.

### **Aim 3: Compare surgical options**

The simulation models will be used to represent two primary surgical options: reconstruction of the medial patellofemoral ligament and realignment of the tibial tuberosity, while also varying parameters related to knee anatomy. The kinematics and pressure output from all the simulated surgical variations will be compared between the 12 models at individual degrees of knee flexion with repeated measures ANOVA's combined with post-hoc Student-Newman-Keuls tests, with significance set at  $p = 0.05$ . The analyses will focus on relative variations in the kinematics and pressure measurements, with the pre-operative condition treated as the control for each knee, with the goal of each procedure to reduce lateral patellar shift and tilt without increasing the contact pressure.

Analyses will be performed for various combinations of tibial tuberosity position and depth of the trochlear groove. For each combination, the statistical analyses noted above will be performed to compare the influence of the various surgical procedures on patellar tracking and contact, with an emphasis on determining the limits at which each procedure becomes ineffective in reducing lateral tracking without overloading cartilage. In addition, for each procedure multivariable linear regression analyses will be performed to relate the anatomical parameters to the change in the output parameters.

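### Aim 3 most naturally reads each procedure's limits from the presence or absence of significance in 12 knees, which cannot show that a procedure is ineffective or that pressure is not raised

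*Combined protocol and SAP*

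**What the plan says.** All references are to the combined protocol and SAP.

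- **Deliverable.** Item 3 of the Specific Aims promises that simulations with varied anatomy "will establish ranges over which each surgical option limits patellar maltracking without elevating contact pressures".
- **Conditions compared.** Item 2 of the Specific Aims says "MPFL reconstruction will be simulated with variations in the femoral attachment position, while the magnitude of tuberosity realignment will be varied". The Aim 3 section of the Approach adds: "The kinematics and pressure output from all the simulated surgical variations will be compared between the 12 models".
- **Test.** The comparison is made "at individual degrees of knee flexion with repeated measures ANOVA's combined with post-hoc Student-Newman-Keuls tests", with significance at p = 0.05. The pre-operative state is each knee's control. The goal is less lateral shift and tilt with no rise in contact pressure, so at least three outputs are judged.
- **Repetition and limits.** "For each combination, the statistical analyses noted above will be performed to compare the influence of the various surgical procedures on patellar tracking and contact", and the same sentence continues "with an emphasis on determining the limits at which each procedure becomes ineffective in reducing lateral tracking without overloading cartilage".
- **Regression.** In a separate, additional sentence, "for each procedure multivariable linear regression analyses will be performed to relate the anatomical parameters to the change in the output parameters". It is not connected to the limits.

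The section names no primary output or angle. It gives no adjustment across angles, outputs or anatomy combinations, no exploratory label, no size of change that marks a limit, and no rule for combining angles and outputs.

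**The concern.** The limits clause belongs to the sentence that reruns the ANOVA and SNK tests for each anatomy combination. The natural reading is therefore that a procedure stops working where its change in shift or tilt is no longer significant, and that it does not overload cartilage where the pressure change is not significant.

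Both inferences treat a non-significant result as evidence of no effect. In 12 knees that is unsafe. The limit would depend on the number of knees as well as on the mechanics, and a real pressure increase could be passed as none. Chance findings in the many repeated tests could also move a limit, in the other direction.

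What is at stake is the interpretation of the simulations. Patients' treatment is not affected, because surgery was to be chosen on clinical evaluation alone.

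**Working it through.** **Inputs from the documents:** 12 knees and p = 0.05. There is no power, effect size or SD to reproduce. **Assumed:** two-sided tests, effect sizes in SDs of the paired change, and the numbers and patterns of conditions and anatomy levels used below.

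**1. Smallest significant paired change.** The threshold is t(0.975; n−1)/√n.
- n = 12: 2.201/√12 = 0.635 SD.
- n = 24: 2.069/√24 = 0.422 SD.

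The thresholds inside the planned ANOVA are similar. With the pooled error and sphericity, SNK requires q(p; df)/√(2n), where p is the number of ordered means spanned. This runs from 0.60 to 0.73 SD with 3 conditions, 0.59 to 0.78 with 4, and 0.58 to 0.82 with 5.

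**2. Power for one unadjusted paired comparison** (noncentral t, 11 df, noncentrality d√12): 35% at d = 0.5, 71% at d = 0.8 and 88% at d = 1.0.

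**3. What a non-significant pressure change means.** An observed rise of 0.5 SD has a 95% interval of 0.5 ± 0.635, or −0.135 to 1.135 SD. It is not significant, yet it is compatible with a rise of more than 1 SD.

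**4. A limit read from loss of significance.** Let the true effect fall in steps of 0.25 SD from 1.5 to 0 over seven anatomy levels, with correlation 0.5 to 0.95 between levels within a knee. Take the first non-significant level as the limit. The share of simulated runs in which the true effect there is still at least 0.5 SD is:

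| Knees | Level per test | Share of runs |
|---|---|---|
| 12 | 0.05 | about 65-70% |
| 24 | 0.05 | about 35% |
| 12 | 0.05/5 = 0.01 | 86-93% |

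The truth is the same in every row. Only the sample size or the test level moves the limit. By contrast, limits from linear fits within each knee (illustrative targets of 0.25 and 0.5 SD) had a median within 0.03 of a level of the truth with 12 or 24 knees, and interval coverage of 94-95%. The simulated truth was linear, which favours this method.

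**5. SNK within one ANOVA.** This is the chance of at least one false pair, with 12 knees and groups of equal means placed far apart.

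| Conditions | Pattern | SNK |
|---|---|---|
| 3 | only pre-op differs | about 5% |
| 5 | only pre-op differs | about 5% |
| 4 | two pairs | 9-10% |
| 5 | pre-op plus two pairs | 9-10% |

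The four-condition figure has a direct check: two separate null pairs, each tested at 5%, give 1 − 0.95² = 9.75%.

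**6. Repetition over angles, outputs and anatomy.** Under a null, several unadjusted tests at 5% give a chance of at least one false finding above 5%. How far above depends on the numbers of angles, combinations and conditions and on their correlations. None of these is stated, so no figure is given.

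**The case against.** - **The nulls are unlikely.** The same 12 models are deliberately altered, so exactly equal means are improbable, and if every variant differs there are no false pairs. This stands, and it is why SNK and the repeated testing are secondary. It does not touch steps 1 to 4, which concern missed effects.
- **A reader might infer a very large family-wise error rate.** The documents do not support a number, because the counts that it needs are not given.
- **A reader might infer that the plan has no multiplicity control at all.** SNK does adjust among conditions within one ANOVA. The gap is across angles, outputs and anatomy combinations, and within an ANOVA only for the patterns in step 5.
- **A reader might infer that the plan is silent on limits, or that it certainly takes them from p-values.** Neither is supported. The control and the direction of benefit are stated, and the regression could supply the limits. However, the wording ties the limits to the tests and not to the regression.
- **The work is exploratory, and the file is abbreviated.** It is a shortened grant application for a simulation study, and one sentence under Aim 1 breaks off, so the angles may be stated elsewhere. That tempers severity. Still, the Aim 3 section sets a significance level and carries no exploratory label, and the aim promises to establish ranges.
- **Adjustment can do harm.** Correct: step 4 shows that a stricter level makes limits read from significance worse. Holm adjustment is therefore acceptable only if limits are never read from it.

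**Conclusion.** The concern holds as a point that should be fixed, with medium confidence. On its most natural reading, the Aim 3 section bases its main deliverable on whether tests in 12 knees reach p = 0.05. That cannot show that a procedure is ineffective or that contact pressure is not increased. The threshold of about 0.64 SD and the 35% power at 0.5 SD follow from n = 12 and a two-sided paired test. The 65-70% figure is an illustration that depends on the assumed decline in effect. If the limits are in fact taken from regression estimates, this risk is smaller, and the plan need only say so.

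The SNK excess (about 9-10% with 4-5 conditions in separated groups of equal means) is conditional. Four or more conditions are likely, because attachment position and realignment magnitude are both varied, but equal means within groups are an assumption. The missing adjustment or label for the repeated tests is real, but its size cannot be given.

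**What to change.** 1. Derive the limits from the estimated change from pre-op in shift, tilt and pressure, with confidence intervals, across tuberosity position and groove depth. Use the planned regression with knee as a repeated unit, since each knee contributes several anatomy combinations. Do not use presence or absence of significance. Judge whether pressure is not increased from the confidence interval. The investigators should state the size of change that defines a limit.
2. Replace SNK with Holm-adjusted paired contrasts: each variant against pre-op, and MPFL reconstruction against tuberosity medialization. Fix the list in advance, and never read limits from these tests.
3. Keep the individual-angle results as estimates with confidence intervals. Behaviour may depend on angle: pressure is analysed "At flexion angles with the patella engaged with the trochlear groove, starting at 15" degrees. Label the angle-by-angle and anatomy-cell tests exploratory.
4. If simulation output has already been seen, say that these choices were made afterwards. The cover letter reports enrollment as complete.

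**Cost.** New wording and some reanalysis of existing output, with no new simulations or patients. Single contrasts lose power: for a 1 SD change in 12 knees, 88% unadjusted against 64% at the first Holm step with 5 contrasts (level 0.01, critical t 3.106).
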